15.1.4. SENSITIVITY ANALYSIS OF PRIMARY EFFICACY VARIABLE

15.1.4.1. ANCOVA

A sensitivity analysis for the primary efficacy variable will be performed using an analysis of covariance (ANCOVA) model on the ITT population. The response variable for the model will be the change from baseline in the MADRS total score at Week 6 (LOCF). The ANCOVA model will include treatment as a categorical factor, pooled study site and the MADRS total score at baseline as a covariate..

Treatment differences for baseline MADRS data will be based on an ANOVA model adjusting for pooled center. Within-treatment post-baseline differences will be assessed with a one-sample t-test using the LS mean and estimated standard error of the mean change from baseline difference. Least square means for each treatment group, the mean difference between treatment groups, the standard error of the mean difference between treatment groups, the associated two-sided 95% CI for the difference between the treatment groups, and p-values for between-treatment tests of differences will be presented. The same pairwise comparisons will be presented as for the MMRM model. Within-group effect size will be calculated as the absolute value of the mean change from baseline divided by the standard deviation of the change from baseline and will be displayed for all post-baseline visits. Between-group effect size will be calculated as the absolute value of the LS mean difference from placebo divided by the model estimate of the pooled standard error (the standard error of the LS mean difference divided by the square root of the sum of inverse treatment group sizes). This analysis will be conducted for the ITT and PP populations. All treatment groups will be included in the ANCOVA models.

15.1.4.2. Random Effects Pattern Mixture Model

A random effects pattern mixture model (Hedeker & Gibbons, 1997) will be applied as one of two sensitivity analyses to explore the robustness of the MMRM results for the primary and key secondary efficacy variables for the ITT population.

Using a random effects PMM, one can examine (a) the degree to which the groups defined by the dropout patterns differ in terms of the outcome variable (i.e., main effect of the dropout pattern variable) and (b) the degree to which the dropout pattern moderates the influence of other model terms (i.e., interactions with the dropout pattern). In deciding on an appropriate grouping of the dropout patterns, an important consideration is the sparseness of the data for each pattern. If a pattern has very few observations, it may not make sense to treat it as a separate group in the analysis. About 82% of randomized patients in the present study were completers as of last patient last visit on 20FEB2017. Hedeker and Gibbons indicated that (Hedeker & Gibbons, 1997) if a large percentage of patients complete the study, it is reasonable to classify patients into completers and dropouts.

Prior to selecting the completer/dropout pattern used above, exploratory analyses were conducted using data from previous SM-13496 schizophrenia studies (D1050229 and D1050233). The completion rates for these schizophrenia studies were 66% for Study D1050229, and 72% for Study D1050233, respectively. The drop out rate for D1002001 is 17.4%. These exploratory analyses involved the following sets of dropout patterns: 1) dropouts and completers, 2) early dropouts, late dropouts, and completers; and, 3) dropouts due to insufficient clinical response and AEs, dropouts due to other reasons, and completers. The overall conclusions from these exploratory analyses were consistent with those from the primary efficacy analyses from the respective studies.

The random effects pattern mixture model will include fixed terms for treatment, time (as a continuous variable), dropout pattern, and two-way interaction terms (i.e., treatment-by-time, dropout pattern-by-treatment, dropout pattern-by-time), and a three-way interaction term (dropout pattern-by-treatment-by-time). The model will also include subject-specific random effects for intercept and time. The response

Document: K:\DSP\SM-13496\KVA95374\Biostatistics\Documentation\SAP

Author:

Version Number:

1.0

Version Date:

30MAR2017

Template No: CS_TP_BS016 – Revision 3

Reference: CS_WI_BS005

Effective Date: 01May2012

Copyright © 2012 [REDACTED] All rights reserved.

The contents of this document are confidential and proprietary to [REDACTED]. Unauthorized use, disclosure or reproduction is strictly prohibited.

variables will be the observed values of the efficacy variables over time, including the baseline value. Patients will be classified into two separate patterns: dropouts and completers. To illustrate, only two treatment groups are considered. Let y_{ij} represent the response value of the i th subject at time j (i.e., actual day of assessment), the following random effects pattern mixture model with an unstructured covariance matrix is fitted:

$$y_{ij} = \beta_0 + \beta_1 Time_{ij} + \beta_2 Treat_i + \beta_3 (Treat_i \times Time_{ij}) + \beta_4 Drop_i + \beta_5 (Drop_i \times Time_{ij}) + \beta_6 (Drop_i \times Treat_i) + \beta_7 (Drop_i \times Treat_i \times Time_{ij}) + v_{0i} + v_{1i} Time_{ij} + \epsilon_{ij} \quad (1)$$

Where:

Drop = 0 for completers, and 1 for dropouts

Treat = 0 for patients in the placebo group, and 1 for patients in the SM-13496 treatment group

The random intercept v_{0i} and random time effect v_{1i} are assumed to follow a bivariate normal distribution, and the model residuals ϵ_{ij} are assumed to be independently distributed and follow a univariate normal distribution.

Based on the above specified random effects pattern mixture model, the parameter estimates for fixed effects (intercept, time, treatment, treatment-by-time, dropout pattern, dropout pattern-by-time, dropout pattern-by-treatment, and dropout pattern-by-treatment-by-time) as well as the covariance matrix for the parameter estimates will be obtained by using the SAS PROC MIXED procedure.

Substituting Drop = 0 and 1 in the above random effects pattern mixture model (1), the following regression models for completers and dropouts can be obtained. The model for completers is:

$$y_{ij} = \beta_0 + \beta_1 Time_{ij} + \beta_2 Treat_i + \beta_3 (Treat_i \times Time_{ij}) + v_{0i} + v_{1i} Time_{ij} + \epsilon_{ij} \quad (2)$$

and the model for dropouts is:

$$y_{ij} = (\beta_0 + \beta_4) + (\beta_1 + \beta_5) Time_{ij} + (\beta_2 + \beta_6) Treat_i + (\beta_3 + \beta_7) (Treat_i \times Time_{ij}) + v_{0i} + v_{1i} Time_{ij} + \epsilon_{ij} \quad (3)$$

Using the estimates from model 1, the parameter estimates for models 2 and 3, i.e., $\beta_k^c = \beta_k$, $\beta_k^d = \beta_k + \beta_{4+k}$ ($k = 0, 1, 2, 3$; c=completers and d=dropouts), for the fixed effects (intercept, time, treatment, and treatment-by-time), as well as the corresponding estimates of the standard errors for these parameter estimates, will be derived for each dropout pattern. The SAS PROC IML procedure can be used for this purpose. In PROC IML, a design matrix is used to create the estimates for completers and dropouts, while an additional design matrix is used to create the overall parameter estimates (intercept, time, treatment, and treatment-by-time) that are a weighted average of the parameter estimates from each dropout pattern:

$$\hat{\beta}_k = \hat{\pi}_k^c \hat{\beta}_k^c + \hat{\pi}_k^d \hat{\beta}_k^d \quad (4)$$

where $k = 0, 1, 2, 3$ denotes the four fixed effects. Weights $\hat{\pi}_k^c$ and $\hat{\pi}_k^d$ are determined based on the proportions of completers and dropouts in the placebo group for $k = 0, 1$ and in the SM-13496 treatment group for $k = 2, 3$. To obtain corresponding estimates of the standard errors for these overall estimates in PROC IML, the

Document:	K:\DSP\SM-13496\KVA95374\Biostatistics\Documentation\SAP		
Author:	[REDACTED]	Version Number:	1.0
		Version Date:	30MAR2017

Template No: CS_TP_BS016 – Revision 3
 Effective Date: 01May2012

Reference: CS_WI_BS005

Copyright © 2012 [REDACTED] All rights reserved. [REDACTED]
 The contents of this document are confidential and proprietary to [REDACTED]. Unauthorized use, disclosure or reproduction is strictly prohibited.

following delta method (Hogan & Laird, 1997) will be used:

$$\hat{V}(\hat{\beta}_k) = (\hat{\pi}_k^c)^2 \hat{V}(\hat{\beta}_k^c) + (\hat{\pi}_k^d)^2 \hat{V}(\hat{\beta}_k^d) + \frac{\hat{\pi}_k^c \hat{\pi}_k^d}{N_k} (\hat{\beta}_k^c - \hat{\beta}_k^d)^2 \quad (5)$$

where N_k is the number of patients in the placebo group for $k = 0, 1$ and in the SM-13496 treatment group for $k = 2, 3$, and $\hat{V}(\hat{\beta}_k)$ denotes the estimate of the variance of $\hat{\beta}_k$ (i.e., the square of its estimated standard error).

Finally, the overall parameter estimates from the random effects pattern mixture model will be compared with the estimates from a random effects model that does not include dropout pattern, but will include fixed terms for treatment, time (as a continuous variable), and a treatment-by-time interaction. This model will also include subject-specific random effects for intercept and time. The random effect model is:

$$y_{ij} = \beta_0 + \beta_1 Time_{ij} + \beta_2 Treat_i + \beta_3 (Treat_i \times Time_{ij}) + v_{oi} + v_{1i} Time_{ij} + \epsilon_{ij} \quad (6)$$

A comparison of the parameters between the above two models helps to assess any impact of missingness (Siddiqui, Hung, & O'Neil, 2009). If the results from these two models are consistent, it implies the MAR assumption is reasonable, because the random effects model without dropout pattern assumes MAR, which is the same assumption that MMRM requires.

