15.1.3. PRIMARY ANALYSIS OF PRIMARY EFFICACY VARIABLE(S)

15.1.3.1. Montgomery-Asberg Depression Rating Scale (MADRS)

The primary efficacy variable is the change from baseline in the MADRS total score at Week 6 for testing superiority of SM-13496 (20-60 or 80-120 mg/day) to placebo, versus the null hypothesis of no difference versus placebo. The hypothesis for each SM-13496 treatment group will be considered independently.

Let μ_{20-60} , μ_{80-120} , and μ_{placebo} represent the mean changes from baseline in the MADRS total score at Week 6 in the 20-60mg, 80-120mg, and placebo groups, respectively. The following 2 hypotheses will be tested to compare the mean changes at Week 6 of each SM-13496 group with that of the placebo group:

- H01: $\mu_{20-60} = \mu_{\text{placebo}}$ versus the alternate H11: $\mu_{20-60} \neq \mu_{\text{placebo}}$.
- H02: $\mu_{80-120} = \mu_{\text{placebo}}$ versus the alternate H12: $\mu_{80-120} \neq \mu_{\text{placebo}}$.

The rater-administered MADRS data will be used for all statistical analyses.

The MMRM method will be used in the ITT population. The MMRM model will include treatment as a categorical factor, visit (Week 1, 2, 3, 4, 5, and 6; as a categorical variable), pooled center, the MADRS total score at baseline as a covariate, and the treatment-by-visit interaction. An unstructured covariance matrix will be used for the within-patient correlation and the Kenward-Rogers approximation will be used to calculate the denominator degree of freedom. In the case of a convergence problem with the unstructured covariance matrix, the following structures with robust sandwich estimator for the standard error of the fixed effect estimates will be assessed in a sequential fashion: heterogeneous Toeplitz, heterogeneous first-order autoregressive, and Toeplitz. Among these 3 covariance structures, the first structure yielding convergence will be used for the MMRM analysis. P-values for comparisons of primary efficacy variable at Week 6 between SM-13496 groups and the placebo group will be adjusted for multiplicity using a Hochberg procedure (section 7.4).

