Document: K:\DSP\SM-13496\KVA95374\Biostatistics\Documentation\SAP
Author: [REDACTED] Version Number: 1.0
Version Date: 30MAR2017

Template No: CS_TP_BS016 – Revision 3 Reference: CS_WI_BS005
Effective Date: 01May2012

Copyright © 2012 [REDACTED] All rights reserved. [REDACTED] Unauthorized use, disclosure or reproduction is strictly prohibited.

```
propcd[1,1] = &grp11/(&grp11+&grp21); /* Completer - control intercept
*/
propcd[2,2] = &grp11/(&grp11+&grp21); /* Completer - control slope
*/
propcd[3,3] = &grp12/(&grp12+&grp22); /* Completer - dose1 intercept
diff */
propcd[4,4] = &grp13/(&grp13+&grp23); /* Completer - dose2 intercept
diff */
propcd[5,5] = &grp12/(&grp12+&grp22); /* Completer - dose1 slope
diff */
propcd[6,6] = &grp13/(&grp13+&grp23); /* Completer - dose2 slope
diff */

propcd[7,7] = &grp21/(&grp11+&grp21); /* Dropout - control
intercept */
propcd[8,8] = &grp21/(&grp11+&grp21); /* Dropout - control slope
*/
propcd[9,9] = &grp22/(&grp12+&grp22); /* Dropout - dose1
intercept diff */
propcd[10,10] = &grp23/(&grp13+&grp23); /* Dropout - dose2
intercept diff */
propcd[11,11] = &grp22/(&grp12+&grp22); /* Dropout - dose1 slope
diff */
propcd[12,12] = &grp23/(&grp13+&grp23); /* Dropout - dose2 slope
diff */

propcdd = J(6,6,0);
propcdd[1,1] = &grp11*&grp21/((&grp11+&grp21)**3);
propcdd[2,2] = &grp11*&grp21/((&grp11+&grp21)**3);
propcdd[3,3] = &grp12*&grp22/((&grp12+&grp22)**3);
propcdd[4,4] = &grp13*&grp23/((&grp13+&grp23)**3);
propcdd[5,5] = &grp12*&grp22/((&grp12+&grp22)**3);
propcdd[6,6] = &grp13*&grp23/((&grp13+&grp23)**3);

meanpm = B*propcd*meancd;
varcpm = B*propcd*varccd*propcd*T(B)
+ propcdd*C*meancd*T(meancd)*T(C);
serrpm = sqrt(vecdiag(varcpm));
zvalpm = meanpm/serrpm;
lowepm=meanpm-1.96*serrpm;
uppepm=meanpm+1.96*serrpm;
probp = 2*(1-PROBNORM(abs(zvalpm)));

CREATE outdata var {meanc serrc lowec uppec probc meand serrd lowed upped
probd meanpm serrpm lowepm uppepm probpm};
append;
close outdata;

QUIT;

*Model repeated without drop out pattern:

PROC MIXED;
CLASS USUBJID;
MODEL AVAL = QSDAY DOSE1 DOSE2 DAY*DOSE1 DAY*DOSE2 /
```

Document: K:\DSP\SM-13496\KVA95374\Biostatistics\Documentation\SAP

Author:

Version Number:

1.0

Version Date:

30MAR2017

Template No: CS_TP_BS016 - Revision 3

Reference: CS_WI_BS005

Effective Date: 01May2012

Copyright © 2012 All rights reserved.

The contents of this document are confidential and proprietary to

Unauthorized use, disclosure or reproduction is strictly prohibited.

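### The random-effects pattern-mixture check of the primary result never forms a Week 6 difference, so it cannot show how far the primary estimate moves when dropout pattern is allowed for

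*SAP*

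**What the plan says.** The target is set in SAP 15.1.3.1: "The primary efficacy variable is the change from baseline in the MADRS total score at Week 6 for testing superiority of SM-13496". The primary MMRM enters "visit (Week 1, 2, 3, 4, 5, and 6; as a categorical variable", so it imposes no curve shape on the Week 6 difference.

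SAP 15.1.4.2 introduces the pattern-mixture model as "one of two sensitivity analyses to explore the robustness of the MMRM results for the primary and key secondary efficacy variables". Its form differs in three ways:

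- The response is the observed score, with baseline counted as one of the responses.
- Time is one continuous term in actual assessment day: "The random effects pattern mixture model will include fixed terms for treatment, time (as a continuous variable), dropout pattern".
- Intercept and slope may differ by arm and by completer/dropout pattern.

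Equation (4) averages four coefficients over the two patterns. In the SAP's words, "an additional design matrix is used to create the overall parameter estimates (intercept, time, treatment, and treatment-by-time) that are a weighted average". Intercept and time are weighted by placebo-arm pattern shares, and the two treatment terms by active-arm shares. Appendix 3 item 3a keeps only the diagonal of the covariance matrix and forms one Wald ratio per coefficient ("zvalpm = meanpm/serrpm").

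The last paragraph of 15.1.4.2 gives the reading rule. The averaged coefficients are compared with those of model (6), which has the same straight-line form without dropout pattern. Agreement is taken to support missing at random.

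**The concern.** A robustness check should let the reader see whether, and by how much, the primary estimate changes under a different treatment of dropout. Here the primary estimate is a difference at Week 6, and the check produces no such quantity.

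Of the two treatment coefficients it reports, one refers to Time = 0. By the study-day convention in SAP 6.1 that is not even an observed day, and it falls beside baseline, where randomisation makes the expected difference about zero. The other is an average slope difference, which equals the Week 6 difference divided by elapsed time only if the arms separate linearly from a common start.

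Comparing with model (6) does not fill the gap. Both models share the straight line, so agreement between them cannot reveal a misfit they have in common, and neither gives a Week 6 figure. A reader could add treatment + 42 × treatment-by-time by hand. The program outputs no covariance between the two, so that sum would have no standard error, and it has the two biases shown in the working.

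**Working it through.** **1. The plan's own figure.** Protocol 3.5 assumes a difference of 3.5 and SD 10, with 161 per group for 80% power to reject both nulls.

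- Mean of each z: 3.5 / (10 × √(2/161)) = 3.14.
- Marginal power: Φ(3.14 − 1.96) = 88.1%.
- Joint power, with correlation 0.5 from the shared placebo arm: 80.4% (80.2% by Monte Carlo).

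The figure reproduces. The SAP states no operating characteristic for the pattern-mixture check.

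**2. What the coefficients mean.** In equation (1) the active-minus-placebo mean at day *t*, within a pattern, is treatment + *t* × treatment-by-time. At *t* = 0 only the treatment term remains, and the comments in Appendix 3 call it an intercept difference. At Week 6 the quantity is treatment + 42 × treatment-by-time. That sum appears in neither the text nor the code.

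**3. How the coefficients behave.** Assumptions: assessments on days −1, 7, 14, 21, 28, 35 and 42; 167 per arm; complete data; two-sided 5%. The documents give no covariance, so two sets were used:

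- A: intercept SD 4.5, slope SD 0.19/day, residual SD 4.
- B: intercept SD 5, slope SD 0.12/day, residual SD 6.

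For A the SD of Week 6 change is √(43² × 0.19² + 2 × 4²) = 9.9. For B it is also 9.9. Both are close to the planned 10.

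With Z holding rows (1, day), V = ZGZ′ + σ²I and δ the true arm-difference curve:

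- expected coefficients: (Z′V⁻¹Z)⁻¹Z′V⁻¹δ
- covariance: (2/n)(Z′V⁻¹Z)⁻¹
- rejection rate: Φ(e/s − 1.96) + Φ(−e/s − 1.96)

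Expected value, then rejection rate under A / B:

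| Assumed true difference | True at Week 6 | Treatment (Time = 0) | 42 × slope | Straight-line Day 42 sum | Unadjusted Week 6 change test |
|---|---|---|---|---|---|
| Linear build-up | −3.5 | −0.08; 5% / 5% | −3.42; 93% / 96% | −3.50; 92% / 97% | 90% |
| Full from Week 1, then flat | −3.5 | −1.87; 90% / 76% | −2.27; 62% / 70% | −4.14; 98% / >99% | 90% |
| Transient (0, −3, −3.5, −3, −2, −1, 0) | 0 | −2.33; 98% / 91% | +1.09; 19% / 22% | −1.24; 22% / 28% | 5% |

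A milder transient (0, −2, −3, −3, −2, −1, 0) with 161 per arm gives 74–89% rejection for the treatment coefficient. A late-onset curve (0, 0, 0, −0.5, −1.5, −2.5, −3.5) gives a straight-line Day 42 sum of −2.94 against a true −3.5. The sum can therefore err in either direction when the difference is curved.

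**4. Would one knot cure the curvature?** Not in general. A Day 14 knot brings the milder transient to −0.19 (5% rejection). For a transient peaking at Week 4 (0, −0.5, −1.5, −3, −3.5, −2, 0) the knotted Day 42 contrast is −1.28 and rejects 22–27% of the time, with a true Week 6 difference of zero.

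**5. Weighting.** Let π_T and π_P be the dropout shares in the active and placebo arms. Combining equation (4)'s two averaged treatment terms omits

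(π_T − π_P) × (placebo dropout mean − placebo completer mean, at Day 42).

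With an assumed 5-point difference in dropout and a 5–10 point gap in means, that is 0.05 × 5 to 0.05 × 10 = 0.25 to 0.5 MADRS points.

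**6. Code against text.** SAP 15.1.4.2 defines Drop as 1 for dropouts. Appendix 3 item 3a sets DROP to 1 when the completion flag is Y, yet labels and weights the DROP = 0 rows as completers. If the group counts follow those labels, the pattern weights are swapped.

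**The case against.** The strongest reply is that the SAP does not use this model to re-test the primary hypothesis. Its stated reading is a comparison of coefficients with model (6), as a diagnostic for missing at random. That stands, and it limits the point. Several stronger readings are tempting:

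- A reader might infer that the treatment p-value acts as a second verdict on the drug and could reject or miss for irrelevant reasons. No section makes it a criterion; it is only computed in Appendix 3.
- A reader might infer that the whole model is unrelated to Week 6. The slope carries the signal when the arms separate roughly linearly (93–96% rejection above).
- A reader might infer that robustness at Week 6 goes unexamined. The placebo-based imputation in 15.1.4.3 refits the primary MMRM. There are also a LOCF ANCOVA and a per-protocol MMRM.
- A reader might infer that the straight line must be wrong because depression scores flatten. The documents give no weekly trajectory (Protocol Table 2 is Week 6 LOCF only), and flattening common to both arms largely cancels. Only curvature in the between-arm difference matters.

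What remains is that 15.1.4.2 also promises to explore the robustness of the MMRM result. A coefficient comparison between two straight-line models does not show what happens to the Week 6 difference.

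**Conclusion.** The concern holds in limited form. The check is offered as support for a Week 6 result but forms no Week 6 quantity, so it cannot show how far the primary estimate moves when dropout pattern is allowed for. This follows from the text and code and needs no assumption.

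The sizes do rest on assumptions about curve shape and covariance, with complete data rather than the SAP's 17.4% dropout. They illustrate what each coefficient measures and do not predict this trial. Under them, the treatment coefficient rejects 5% of the time for a linear −3.5 effect and 91–98% for a transient one that has ended. The slope ranges from a good proxy to one of the opposite sign.

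The primary test and its type I error are untouched. The documents do not support saying that the primary conclusion could be overturned by this analysis, or that it lacks any other Week 6 check. This is a worthwhile, cheap correction to a supporting analysis.

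**What to change.** In SAP 15.1.4.2 and Appendix 3 item 3a:

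1. For each arm, form the pattern-weighted Day 42 mean using that arm's own completer and dropout proportions, then subtract placebo. Take the standard error by the delta method: the contrast's variance from the full fixed-effect covariance, plus, for each arm, (completer share × dropout share / N) × (completer mean − dropout mean)² at Day 42.
2. Report this difference and its 95% CI beside the MMRM Week 6 difference and beside the same contrast from model (6).
3. Relax linearity where the dropout pattern's data allow, for example with a knot or quadratic term, and state the shape assumption that remains. Do not treat a Day 14 knot as generally unbiased. The dropout pattern is small (0.174 × 167 ≈ 29 per arm), patients who leave before a knot tell nothing about the line after it, and their Day 42 mean is an extrapolation under any of these models.
4. Do not present the Time = 0 treatment p-value as evidence of drug effect.
5. In the same edit, reconcile the code's DROP coding with the text.

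The cost is SAP wording and some extra MIXED and IML code, with no new data. The fixed-effect covariance is already read into PROC IML. Relaxing linearity widens the interval somewhat. With complete data and a linear effect the knot costs about 1 point of power or less. In simulation with 17.4% dropout, the knotted contrast rejected about 69–77% of the time against 71–89% for the straight line, at −3.5 with linear or exponential onset.

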4.2 Method of assigning patients to treatment groups

[REDACTED], the Interactive Web Response System (IWRS) vendor, is responsible for generating the randomization code by computer software incorporating a random number generator. The allocation ratio is 1:1:1 (20-60 mg: 80-120 mg: placebo).

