7.2. MULTICENTER STUDIES

This study will be conducted by multiple investigators at multiple centers internationally.

All centers with eleven or fewer randomized patients will be pooled by size within country or geographic region. No pooled center will contain more than 25 randomized patients. If the pooling cannot be performed within country, other centers in the same geographic region will be considered. The list of pooled centers for the present study based on the pooling strategy previously described is provided in Table B.

Table B: Pooled Sites

Document:	K:\DSP\SM-13496\KVA95374\Biostatistics\Documentation\SAP		
Author:	[REDACTED]	Version Number:	1.0
		Version Date:	30MAR2017

Template No: CS_TP_BS016 – Revision 3
Effective Date: 01May2012

Reference: CS_WI_BS005

Copyright © 2012 [REDACTED] All rights reserved. [REDACTED]
The contents of this document are confidential and proprietary to [REDACTED]. Unauthorized use, disclosure or reproduction is strictly prohibited.

Pooled Center ID	Center ID (Number of Subjects)	Country	Number of Subjects
901		JPN	21
902		JPN	21
903		JPN	13
904		JPN	23
905		JPN	22
906		JPN	22
907		JPN	24
908		JPN	17
909		JPN	16
910		LTU	22
		RUS	
911		MYS	19
912		PHL	24
		TWN	
913		RUS	22
914		RUS	24
915		RUS	17
916		RUS	24
917		RUS	18
918		RUS	13
919		RUS	15
920		SVK	16
921		UKR	19
922		UKR	17
923		UKR	17
924		UKR	15
925		UKR	15
926		UKR	14
927		UKR	13
928		UKR	21

A term for treatment by pooled center interaction will not be included in the primary analysis model, however, a sensitivity analysis, based on the primary model but including a term for treatment by pooled center interaction, will be performed.

Document: K:\DSP\SM-13496\KVA95374\Biostatistics\Documentation\SAP
 Author: [REDACTED] Version Number: 1.0
 Version Date: 30MAR2017

Template No: CS_TP_BS016 – Revision 3 Reference: CS_WI_BS005
 Effective Date: 01May2012

Copyright © 2012 [REDACTED] All rights reserved. [REDACTED] Unauthorized use, disclosure or reproduction is strictly prohibited.

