APPENDIX 3. SAS CODE

Treatment: TRTPN
Analysis visit: AVISIT

1. Mixed Model Repeated Measures (MMRM) Analysis

Note: Ensure that input dataset is sorted by USUBJID AVISIT prior to initiating the MIXED procedure.

```
ods output estimates=outset /*Output from estimate statement*/  
diffs=outdiff /*Treatment Group Comparison*/  
R=outr /*R matrix */  
lsmeans=outlsmean; /*LSmeans of each treatment group*/
```

```
PROC MIXED;  
CLASS SUBJID POOLSITE TRTPN AVISIT;  
MODEL CFB = BASE POOLSITE TRTPN AVISIT TRTPN*AVISIT/DDFM=KR;  
REPEATED AVISIT /TYPE=UN SUBJECT=SUBJID R;  
LSMEANS TRTPN* AVISIT /PDIFF CL;  
ESTIMATE 'LINEAR TREND TEST FOR DOSE RESPONSE'  
TRTPN 0 1 -1 TRTPN*AVISIT 0 0 0 0 0 0 0 0 0 0 0 0 0 1  
0 0 0 0 0 0 -1/CL;  
ESTIMATE 'DOSE-RESPONSE 20-60 vs 80-120' TRTPN -1 1 0 TRTPN*AVISIT  
0 0 0 0 0 0 -1 0 0 0 0 0 0 1 0 0 0 0 0 0 0/CL;  
RUN;
```

a. Mixed Model Repeated Measures (MMRM) Analysis for the case above
model fails to converge

```
PROC MIXED empirical;
```

Document:	K:\DSP\SM-13496\KVA95374\Biostatistics\Documentation\SAP	Version Number:	1.0
Author:	[REDACTED]	Version Date:	30MAR2017

Template No: CS_TP_BS016 – Revision 3
Effective Date: 01May2012

Reference: CS_WI_BS005

Copyright © 2012 [REDACTED] All rights reserved.
The contents of this document are confidential and proprietary to [REDACTED]. Unauthorized use, disclosure or reproduction is strictly prohibited.

```
CLASS SUBJID POOLSITE TRTPN AVISIT;  
MODEL TOTCFB = TOTBL POOLSITE TRTPN AVISIT TRTPN*AVISIT;  
REPEATED AVISIT /TYPE=XXX SUBJECT=SUBJID R;  
LSMEANS TRTPN*AVISIT /PDIFF CL;  
ESTIMATE 'LINEAR TREND TEST FOR DOSE RESPONSE'  
TRTPN 0 1 -1 TRTPN*AVISIT 0 0 0 0 0 0 0 0 0 0 0 0 1  
0 0 0 0 0 0 -1/CL;  
ESTIMATE 'DOSE-RESPONSE 20 vs 80-160' TRTPN -1 1 0 TRTPN*  
AVISIT 0 0 0 0 0 0 -1 0 0 0 0 0 0 1 0 0 0 0 0 0/CL;  
RUN;
```

XXX: application order
Heterogeneous Toeplitz (TYPE=TOEPH)
Heterogeneous first-order autoregressive (TYPE=ARH(1))
Toeplitz (TYPE=TOEP)

2. Analysis of Covariance

```
PROC MIXED;  
CLASS TRTPN POOLSITE;  
MODEL CFB = TRTPN POOLSITE BASE;  
LSMEANS TRTPN / PDIFF CL;  
ESTIMATE 'LINEAR TREND' TRTPN 0 1 -1 /CL;  
ESTIMATE 'DOSE-RESPONSE 20 vs 80-160' TRTPN -1 1 0/CL;  
RUN;
```

3. Sensitivity Analysis

a. Random Effects Pattern Model

```
If TRT01PN=1 then DOSE1=1 else DOSE1=0;  
If TRT01PN=2 then DOSE2=1 else DOSE2=0;  
If COMPLFL="Y" then DROP=1 else DROP=0;
```

```
PROC MIXED;  
CLASS USUBJID;  
MODEL AVAL = QSDAY DOSE1 DOSE2 QSDAY*DOSE1 QSDAY*DOSE2  

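### SAP 15.1.4.2: equation (4) weights the treatment terms by the active arm's pattern shares only, so comparing them with model (6) mixes a weighting difference into a check on missing at random

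*SAP*

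**What the plan says.** SAP 15.1.4.2 fits model (1), with treatment, time, dropout pattern and all their interactions. It derives the completer and dropout equations (2) and (3), and equation (4) averages each coefficient over the two patterns. The weights are the proportions of "completers and dropouts in the placebo group for $k = 0, 1$ and in the SM-13496 treatment group for $k = 2, 3". Appendix 3 does the same dose by dose, for example "propcd[5,5] = &grp12/(&grp12+&grp22); /* Completer - dose1 slope"; no placebo count enters the weights for the treatment intercept or slope differences.

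The overall estimates are then set beside model (6), which contains treatment, time and their interaction but no pattern. The stated reading is: "If the results from these two models are consistent, it implies the MAR assumption is reasonable". No threshold is given.

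Dropout is reported for all arms together: "The drop out rate for D1002001 is 17.4"%. The text defines "Drop = 0 for completers, and 1 for dropouts", whereas Appendix 3 prints "If COMPLFL='Y' then DROP=1 else DROP=0".

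**The concern.** Model (6) estimates the difference between whole arms. Equation (4) for k = 2, 3 estimates a within-pattern treatment contrast averaged over the active arm's mix of completers and dropouts. Both are legitimate and the weights are disclosed, but they are different quantities whenever the arms differ in dropout and the placebo patterns differ in outcome. The SAP nonetheless uses their agreement as evidence about the missing-data mechanism. What is at stake is a misreading of one supportive analysis: part of any agreement or disagreement may come from the weights.

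**Working it through.** **Algebra.** From models (2) and (3), weighting each arm's patterns by that arm's own shares and subtracting gives

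marginal difference at time t = (b2 + b3·t) + piA(b6 + b7·t) + (piA − piP)(b4 + b5·t).

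Equation (4) for k = 2, 3 returns the first two parts only. The third is the imbalance in dropout times the placebo dropout-minus-completer gap. It is zero if dropout is equal or the gap is zero. The placebo terms (k = 0, 1) use placebo shares and have the same target as model (6).

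**Nothing missing.** With complete balanced data, model (6) reproduces the observed arm means, so equation (4) should miss it by −(piA − piP) × gap. Simulated complete data with response-related pattern labels confirm this. At 14%/19% dropout (placebo/active) and a gap of 10.6, the difference at Week 6 is −0.05 × 10.6 = −0.53. At 24%/14% and a gap of 9.5 it is +0.10 × 9.5 = +0.95. Arm-specific weighting matches model (6) exactly. MAR cannot be the cause, since nothing is missing.

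**Size of the omitted term (gaps and imbalances assumed), in MADRS points at Week 6:**

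| Imbalance | gap 4 | gap 8 | gap 12 |
|---|---|---|---|
| 3 points | 0.12 | 0.24 | 0.36 |
| 5 points | 0.2 | 0.4 | 0.6 |
| 10 points | 0.4 | 0.8 | 1.2 |

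**Under MAR with truncated follow-up.** Model (6) also extrapolates, so its distance from equation (4) is smaller than the omitted term. Simulation assumptions: 175 per arm, one active arm and placebo, visits at Weeks 0 to 6, intercept SD 4, slope SD 8 per 6 weeks, residual SD 3, dropout driven by the last observed change, REML, 300 trials, Monte Carlo SE 0.01 to 0.03. Week 6 estimate minus model (6):

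| Setting | Dropout, placebo/active | Equation (4) | Arm-specific |
|---|---|---|---|
| No effect, gap about 10 | 17%/17% | −0.02 | −0.01 |
| | 14%/19% | −0.30 | +0.18 |
| | 11%/20% | −0.57 | +0.39 |
| | 20%/15% | +0.25 | −0.22 |
| | 24%/14% | +0.51 | −0.43 |
| No effect, gap about 6 | 14%/19% | −0.19 | +0.12 |
| | 11%/21% | −0.37 | +0.24 |
| True effect −3.5 | 11%/20% | −0.48 | +0.47 |
| | 24%/14% | +0.57 | −0.37 |
| | 10%/16% | −0.27 | +0.31 |

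The equation (4) differences of 0.19 to 0.57 are 5% to 16% of the 3.5-point design difference in Protocol 3.5. A separate large-sample run (60,000 per arm) gave 0.20 to 0.51 for 5- and 10-point imbalances with gaps of about 9 to 10. Stronger dependence of dropout on response (gaps of about 16 to 17) gave up to 0.95. When dropout did not depend on response, the difference was at most 0.02.

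**How likely is imbalance?** Protocol 4.2 says "The allocation ratio is 1:1:1 (20-60 mg: 80-120 mg: placebo"). SAP 7.2 describes Table B in terms of randomized patients ("No pooled center will contain more than 25 randomized patients"), and its 28 rows sum to 524; 0.174 × 524 ≈ 91 dropouts. Spreading 91 at random over arms of 175/175/174 gives an SD of 4.1 points per active-placebo comparison. The chance that at least one of the two is off by 5 points or more is 38%, and by 10 or more about 2%.

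This model uses the ITT population, which excludes patients without a post-baseline MADRS. Protocol 3.5 allows for (501 − 483)/501 = 3.6%, or about 19 of 524. Counting those as dropouts leaves 72 of 505, an SD of 3.8 points and a 31% chance of a 5-point imbalance.

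**The case against.** The strongest reply is that arm-specific weighting is not shown to make a better MAR check. That stands. Under MAR its distance from model (6) is of similar size, in the opposite direction, and sometimes larger (+0.31 against −0.27 at 10%/16%). Its advantage is in the target: when model (1) is itself true with a marginal difference of +0.40 (14%/19%, gap 8), it gives +0.45, model (6) +0.31 and equation (4) +0.06.

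It is also fair that weighting is only one source of disagreement. Even the correctly weighted placebo Week 6 mean differed from model (6) by 0.29 to 1.07 points under MAR, so the sentence on MAR needs softening whatever the weights.

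The effect is modest beside the SE of 1.10 for the treatment difference in the earlier monotherapy study (Protocol 3.5, Table 2). MAR is also probed by placebo-based imputation (SAP 15.1.4.3) and the plot by visit of discontinuation (15.1.3.1), and LOCF ANCOVA is a further sensitivity analysis.

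A reader might infer more than the documents support:
- *That benefit is overstated.* The sign follows the direction of the imbalance, which is unknown.
- *That the weights hide a departure from MAR.* Cancellation is algebraically possible, but no simulated case showed it.
- *That the DROP coding adds to this effect.* It is a separate contradiction. As printed, the completer and dropout labels are reversed; whether the weights are reversed too depends on the grp macro counts, which the SAP does not define.

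**Conclusion.** The concern holds as a minor point. For k = 2, 3 the comparison with model (6) sets two different treatment contrasts side by side, and their difference includes (piA − piP)(b4 + b5·time), which carries no information about MAR. It needs both unequal dropout by arm and a placebo completer-dropout gap. Neither is in the documents, so all sizes are conditional: about 0.1 to 1.2 points for the omitted term, and about 0.2 to 0.6 for the distance from model (6) under MAR at imbalances of roughly 5 to 10 points with fitted gaps of about 6 to 10. Equal underlying dropout would still leave a 31% to 38% chance of a 5-point imbalance in at least one comparison. Equation (4) is not invalid; the inference drawn from the comparison is. The primary MMRM and its Hochberg tests do not depend on it.

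**What to change.** 1. Correct the DROP line in Appendix 3 to agree with 15.1.4.2, and define the grp counts so that labels and weights match. This is needed whatever is decided on the weights.
2. Replace the sentence on MAR: agreement with model (6) is supportive only, and disagreement does not by itself show a departure from MAR.
3. Label the k = 2, 3 output of equation (4) as a within-pattern contrast averaged over the active arm's pattern mix, and show dropout by arm beside it.
4. Next to it, report the arm-specific difference: average each arm's intercept and slope over its own shares, then subtract. State that it shares model (6)'s target but is not a clean test of MAR.

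Step 4 needs more than one extra variance term. The averaging matrix must change so that placebo coefficients enter the treatment rows. The active-arm proportion term in equation (5) must use the active dropout-completer difference (b4 + b6 for the intercept, b5 + b7 for the slope) in place of b6 and b7. A placebo term, piP(1 − piP)/NP times the squared placebo difference (b4 or b5), must be added. The whole change is a few lines of PROC IML, one coding line, one label and one sentence, with no new data.
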